## 16. Advisory Committees

### 16.1. Data Monitoring Committee

A Data Monitoring Committee (DMC) will not be utilized for this clinical study as no interventions intended to prolong life or reduce risk of a major adverse health outcome (e.g., cardiovascular events) are evaluated, for which favorable or unfavorable study results suggest study termination. Additionally, there are no safety concerns suggesting the need for a DMC. This study is considered non-significant risk for study participants, thus the need for additional safety oversight beyond Medtronic's already rigorous safety monitoring processes is not required. Finally, this study does not have a pre-specified interim analysis.

This document is electronically controlled. Printed copies are considered uncontrolled.

**Confidential**

Protocol #: COVMOPO0561

Rev E 09AUG2017

**Confidential**

## 1. Version History

Version	Summary of Changes	Author(s)/Title
1.0	
 
New Document
 
	██████████
2.0	
 
Remove the CIP version reference in title page
 
	██████████

## 2. List of Abbreviations and Definitions of Terms

Term	Abbreviation	Definition
Adverse Event	AE	
Any untoward medical occurrence, unintended disease or injury, or untoward clinical signs (including abnormal laboratory findings) in subjects, users or other persons, whether or not related to the medical device.
 
NOTE 1: This definition includes events related to the medical device or the comparator.
 
NOTE 2: This definition includes events related to the procedures involved.
 
NOTE 3: For users or other persons, this definition is restricted to events related to the medical devices.

American Heart Association	AHA	
A non-profit organization in the United States that fosters appropriate cardiac care in an effort to reduce disability and deaths caused by cardiovascular disease and stroke.
 
The AHA published guidelines in 2003 for telemetry monitoring that are still applicable and being used currently.

Adverse Device Effect	ADE	Adverse event related to the use of a medical device.
Clinical Investigation Plan	CIP	The present document describing the study protocol.
CIP Deviation	CIP Deviation	An event when the investigator or site personnel did not conduct the study according to the CIP or the clinical trial agreement. Medtronic's term for protocol deviation.

This document is electronically controlled. Printed copies are considered uncontrolled.

**Confidential**

Term	Abbreviation	Definition
Case Report Forms / Electronic CRF	CRF/eCRF	Forms where the clinical data are collected. eCRF is the electronic version of the CRF.
Device Deficiency	DD	Inadequacy of a medical device with respect to its identity, quality, durability, reliability, safety or performance.  NOTE 1: This definition includes adverse events resulting from insufficient or inadequate instructions for use, deployment, implantation, installation, or operation, or any malfunction of the medical device.  NOTE 2: This definition includes any event resulting from use error or from intentional misuse of the medical device
Electrocardiogram	ECG	A clinical technique measuring transthoracic electrical activity of the heart over time.
Electronic Data Capture	EDC	Electronic system where the data are collected through the eCRF (Oracle Clinical). May also be referred to as RDC (Remote Data Capture).
Emergency Department	ED	Medical treatment facility specializing in emergency medicine, the acute care of patients who present without prior appointment; either by their own means or by that of an ambulance.
Electronic Medical Record	eMR	Digital version of a patient's medical record within a single facility.
Food and Drug Administration	FDA	Federal agency of the United States Department of Health and Human Services; regulates medical devices.
Heart Rate	HR	A unit of measure that indicates speed of heartbeat in beats per minute.
Intensive Care Unit	ICU	A hospital unit with concentrated special equipment and specially trained personnel for the care of seriously ill patients requiring immediate and continuous attention.

This document is electronically controlled. Printed copies are considered uncontrolled.

**Confidential**

Term	Abbreviation	Definition
Informatics Manager	IM	A type of software that is intended to route and store medical device data and device diagnostic information from supported devices to the VPMP, 3rd Party Annunciation Systems, Electronic Medical Record (eMR) and Clinical Information System (CIS).
Institutional Review Board	IRB	An independent body in US, consisting of healthcare professionals and non-medical members, whose responsibility is to protect rights, safety and well-being of human subjects involved in a clinical trial and to provide public assurance of that protection, by, among other things, expressing an opinion on the clinical trial protocol, the suitability of the investigators involved in the trial and the adequacy of facilities, and on the methods and documents to be used to inform trial subjects and obtain their informed consent.
Investigator Site File	ISF	Regulatory binder supplied by the sponsor.
Length of stay	LOS	The overall hospital length of stay, time of admission to discharge.
Post-anesthesia care unit	PACU	Hospital units typically attached to an operating suite that provide care to patients recovering from anesthesia
Product Accountability Log	PAL	A log maintained by investigative site personnel to document that the study product(s) have been used according to the protocol, and to document the final accounting of study product(s) received at the site, dispensed to subjects, returned by the subjects, and returned to the sponsor.
Patient-controlled analgesia	PCA	A drug-delivery system that dispenses a preset intravascular dose of a narcotic analgesic when the patient pushes a switch on an electric cord.
Rapid Response Team	RRT	A team of health care providers that responds to hospitalized patients with early signs of clinical deterioration on non-intensive care units to prevent respiratory or cardiac arrest.

This document is electronically controlled. Printed copies are considered uncontrolled.

**Confidential**

Term	Abbreviation	Definition
Respiration Rate	RR	A unit of measure that indicates rate of breathing in breaths per minute.
Serious Adverse Event	SAE	
Adverse event that
 
 
1. led to death,
 
2. led to serious deterioration in the health of the subject, that either resulted in               
 
a. a life-threatening illness or injury, or
 
b. a permanent impairment of a body structure or a body function, or
 
c. in-patient or prolonged hospitalization, or
 
d. medical or surgical intervention to prevent life-threatening illness or injury or permanent impairment to a body structure or a body function,
 
 
 
3. led to fetal distress, fetal death or a congenital abnormality or birth defect
 
 
Note: Planned hospitalization for a pre-existing condition, or a procedure required by the protocol, without serious deterioration in health, is not considered a serious adverse event.

Serious Adverse Device Effect	SADE	Adverse device effect that has resulted in any of the consequences characteristic of a serious adverse event.
Surveillance Monitoring	SM	The SM group will serve as the group who will be monitored by the study device for the duration of study enrollment on a medical-surgical unit(s).
Standard Operating Procedures	SOP	Medtronic Quality Standard Operating Procedures
Telemetry Monitoring	TM	The TM group will serve as the control group in this study and will be monitored via the site's standard of care telemetry practice/protocol.
Vital Sync™ Informatics Manager & Virtual Patient	Vital Sync™ IM & VPMP	A software only device that provides mobile and centralized remote monitoring.

This document is electronically controlled. Printed copies are considered uncontrolled.

**Confidential**

Term	Abbreviation	Definition
Monitoring Platform		
Virtual Patient Monitoring Platform	VPMP	A display system that provides visual and audible renderings of physiologic data, waveforms, alarms and alerts routed through the Vital Sync™ IM from supported devices. The Vital Sync™ VPMP displays information received from the IM on any web-enabled device.

### 3. Introduction

This is a single-center, prospective, pilot, pre/post implementation study to collect post-market data on hospitalized subjects monitored via telemetry monitoring and surveillance monitoring.

The purpose of the study is to evaluate the impact of surveillance monitoring versus telemetry monitoring on clinical, healthcare economics, resource utilization, and qualitative outcomes.

### 4. Study Objectives

#### 4.1. Objectives

##### 4.1.1. Primary Objective

The primary objective of this study is to compare hospital length of stay (LOS) between the surveillance monitoring and telemetry monitoring period on patients without AHA telemetry indication.

##### 4.1.2. Secondary Healthcare Economic and Resource Utilization Objectives

1. Compare telemetry bed, emergency department (ED) bed, and intensive care unit (ICU) bed availability between monitoring periods
2. Compare associated health care costs between monitoring periods
3. Compare the number of ICU, ED, PACU, and telemetry delays in transfer between monitoring periods
4. Compare the number of hospital unit transfers between monitoring groups
5. Compare the number of unplanned ICU transfers between monitoring groups
6. Compare ICU LOS for subjects having unplanned transfers to the ICU between monitoring groups
7. Compare the number of unnecessary diagnostic tests and therapeutic procedures generated by artifacts and/or misdiagnosis between monitoring groups

##### 4.1.3. Secondary Clinical and Qualitative Objectives

1. Compare the number of Rapid Response Team (RRT) interventions between monitoring groups
2. Compare survival rates post RRT interventions between monitoring groups
3. Compare code blue rates between monitoring groups

This document is electronically controlled. Printed copies are considered uncontrolled.

**Confidential**

4. Compare unplanned intubations between monitoring groups
5. Compare time of RRT activation to time of threshold notifications from SM system following clinical deterioration events
6. Assess clinical team satisfaction with surveillance monitoring and study product
7. Assess patient satisfaction with surveillance monitoring and study product
8. Assess perceptions of clinicians who prescribe telemetry to patients without AHA indication
9. Assess clinicians' perceptions on telemetry utilization and impact on hospital resource utilization and patient flow

## 4.2. Endpoints

### 4.2.1. Definition of Primary Endpoint

1. Length of stay

**Definition:** The overall hospital LOS; time (in minutes) of admission to discharge during indexed hospitalization.

### 4.2.2. Definition of Secondary Healthcare Economic and Resource Utilization Endpoints

1. Telemetry bed, ED, and ICU bed availability

**Definition:** Daily available number of beds available in both telemetry ED, and the ICU measured daily in hours from 12:00 AM to 11:59 PM.

2. Associated health care costs

**Definition:** Costs attributable to the primary and secondary clinical and resource utilization endpoints.

3. ICU, ED, PACU, and telemetry delays in transfer

**Definition:** Number of patients delayed admission to the ICU, ED, PACU, and to a telemetry bed.

4. Hospital unit transfers

**Definition:** Number of inpatient transfers from one unit to another unit during course of hospital stay.

5. Unplanned ICU transfers

**Definition:** Direct transfers from either study monitoring group to the ICU where the transfer was not planned during the hospital stay. For example, a transfer may be planned in advance of certain procedures for high risk patient as a preventative measure. The study team will determine if transfer were considered planned versus unplanned by review of the medical record.

6. LOS for ICU transfers

**Definition:** The LOS (time in minutes) in the ICU for subjects who have an unplanned transfer to the ICU.

7. Diagnostic tests and therapeutic procedures generated by artifacts and/or misdiagnosis

This document is electronically controlled. Printed copies are considered uncontrolled.

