#### 6.1.2. Secondary Healthcare Economic and Resource Utilization Objectives

1. Compare telemetry bed, emergency department (ED) bed, and intensive care unit (ICU) bed availability between monitoring periods
2. Compare associated health care costs between monitoring periods
3. Compare the number of ICU, ED, PACU, and telemetry delays in transfer between monitoring periods
4. Compare the number of hospital unit transfers between monitoring groups
5. Compare the number of unplanned ICU transfers between monitoring groups
6. Compare ICU LOS for subjects having unplanned transfers to the ICU between monitoring groups
7. Compare the number of unnecessary diagnostic tests and therapeutic procedures generated by artifacts and/or misdiagnosis between monitoring groups

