### 7.1. Duration

The planned duration of the study is greater than or equal to six months. The control (TM) group will complete enrollment first over an estimated three month period, followed by an estimated three month enrollment period for the SM group.

Subject participation will last less than or equal to the duration of the hospital stay. Each subject will be followed in the hospital for a maximum period of 30 days ( $\pm$  2 days) from the start of enrollment.

No follow-up will occur after subjects are discharged from the hospital.

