**Confidential**

Subjects who meet all of the inclusion criteria and none of the exclusion criteria will be assigned to either one of the monitoring groups and then followed for the duration of their hospital stay.

[figure not shown]
The subject population will include up to a total of 280 subjects with up to 140 subjects in each monitoring group.

Each enrolled subject will be assigned to one of two types of monitoring arms: telemetry monitoring (TM) OR surveillance monitoring (SM) and then followed for the duration of their hospital stay up to 30 days ( $\pm$  2 days). The monitoring groups described in Section 10.1 of CIP will be enrolled in two prospective phases. The enrollment phase of the TM group will occur first. After TM subjects have completed study participation, the SM phase will initiate. Study flowchart is reported in Figure 1.

No randomization will be used during the course of the study. Assignment to a monitoring arm will be determined by the phase status of the study. During the TM phase, all subjects will be assigned to the TM group. During the SM phase, all subjects will be assigned to the SM group.

No blinding and interim analysis will occur during the course of the study.

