**Confidential**

## 7.2. General Methodology

In general, descriptive statistics will be used to summarize baseline and study outcomes. For continuous variables, number of available observations, mean, standard deviation, median, minimum and maximum values will be provided. For categorical variables, frequency and percentage will be used. Unless otherwise specified, statistical assessments will be based on 2-sided tests at an alpha level of 0.05, which include Student-t or Wilcoxon rank-sum or ANOVA test for continuous variables, and Chi-square or Fisher's exact test for categorical variables. Multivariate regression models will be used to assess impacts of potential confounding variable. Statistical analysis will be performed using [REDACTED] (SAS Institute Inc., Cary, NC) or other valid statistical software.

The primary effectiveness analysis will be based on all evaluable data from this study. A per protocol analysis will be performed based on all subjects who are compliant with the study protocol, i.e. who provide valid informed consents and do not experience any major protocol deviations.

For safety assessments, adverse events (AEs) will be summarized using frequency counts and percentages. Descriptive statistics will be provided by monitoring group and by severity and relationship. Additionally, differences between the two monitoring groups will be summarized along with 95% confidence intervals. Individual listings of adverse events, including event type, start date, duration, severity, and device-relatedness will be provided as appropriate. The safety analysis will be based on all patients participated in the study.

Further, a health economic analysis will be performed based on healthcare economic and resource utilization data collected in this study. Monitoring effectiveness, QoL in the form of Quality-Adjusted Life-Years (QALYs), life-years gained and other data collected in this study may be used as inputs to the model.

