## 7.3. Center Pooling

N/A – This is a single-center study.

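### Daily bed availability is a time series, but the SAP's default two-sample tests treat its days as independent and ignore day of week, so the p-values would be miscalibrated

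*SAP*

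**What the plan says.** The first secondary economic objective (Protocol 6.1.2, repeated in SAP 4.1.2) is to "Compare telemetry bed, emergency department (ED) bed, and intensive care unit (ICU) bed availability between monitoring periods". The endpoint (SAP 4.2.2, same definition in Protocol 6.2.2) is "Daily available number of beds available in both telemetry ED, and the ICU measured daily in hours from 12:00 AM to 11:59 PM". The unit of comparison is therefore the period, not the subject.

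On timing, Protocol 7.1 states: "The control (TM) group will complete enrollment first over an estimated three month period, followed by an estimated three month enrollment period for the SM". Here SM is the surveillance arm. SAP section 5 adds: "After TM subjects have completed study participation, the SM phase will initiate". SAP 7.3 confirms: "This is a single-center study".

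On method, SAP 7.9 lists the endpoint without an analysis. The general rule in SAP 7.2 for continuous variables, where nothing else is specified, is that "statistical assessments will be based on 2-sided tests at an alpha level of 0.05, which include Student-t or Wilcoxon rank-sum or ANOVA test". The only modelling provision there is "Multivariate regression models will be used to assess impacts of potential confounding variable". SAP 7.2 also promises a health economic analysis using resource utilization data but gives no method for this endpoint, and SAP 7.11 (Health Outcomes Analyses) is marked not applicable. Neither document mentions serial correlation, time-series methods, robust standard errors or day of week.

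**The concern.** With one hospital and one value per day, each unit (telemetry, ED, ICU) contributes a single series of roughly 90 values per period. A patient who stays overnight holds the same bed on consecutive days, so one day's free beds help to predict the next day's. The t, Wilcoxon and ANOVA tests assume independent observations. When days are positively correlated, a period mean varies more than the day-to-day spread suggests, and the test rejects too often.

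The same tests also ignore any weekday/weekend pattern. That pattern adds to the day-to-day spread but falls almost equally on both periods, which pushes the error the other way. With both features unmodelled, a nominal 5% p-value has no known error rate.

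At stake is how far a reported change in bed availability can be believed. More free beds is part of the argument for surveillance monitoring in Protocol 5.1, publication is planned (Protocol 15.9), and SAP 7.5 makes no adjustment for multiple comparisons.

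**Working it through.** **The plan's own figures.** None is given for bed availability. The only computable figure is the primary sample size. On the log scale the standard deviation is sqrt(ln(1 + 0.65²)) = 0.5936 and the margin is ln(1.2) = 0.1823. At one-sided 0.05 and 80% power, n = 2 × (1.645 + 0.842)² × 0.5936² / 0.1823² ≈ 131.1, so 132 per group, as stated. This concerns length of stay and does not bear on the present point.

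**Inputs.**
- Days per period: n = 90, from the estimated three months (Protocol 7.1).
- Test: two-sided 0.05 (SAP 7.2).
- Lag-1 correlation ρ: not in the documents; assumed AR(1) with ρ from 0.2 to 0.7.
- Share w of daily variance due to a fixed weekly cycle: not in the documents; assumed 0, 30% or 50%.
- No true difference between periods.

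**Step 1: variance inflation of a period mean.** VIF = 1 + 2 × Σ (1 − k/n) ρ^k, for k = 1 to n − 1. The effective number of days is n / VIF. At ρ = 0.5, VIF = 2.96, so 90 days carry the information of about 30.

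**Step 2: actual error with no weekly cycle.** Error = 2 × [1 − Φ(1.96 / sqrt(VIF))]. At ρ = 0.5 this is 2 × [1 − Φ(1.14)] ≈ 25%.

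**Step 3: adding a weekly cycle.** The cycle enters the naive day-to-day variance but nearly cancels between two periods of almost 13 weeks. Only the share (1 − w) contributes to random variation of the difference, so VIF is replaced by VIF × (1 − w). At ρ = 0.2 and w = 0.3: 1.49 × 0.7 = 1.04, error 5.5%.

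| ρ | VIF | Effective days | Error, w = 0 | Error, w = 30% | Error, w = 50% |
|---|---|---|---|---|---|
| 0.2 | 1.49 | 60 | 10.9% | 5.5% | 2.3% |
| 0.3 | 1.84 | 49 | 14.9% | 8.4% | 4.1% |
| 0.5 | 2.96 | 30 | 25.4% | 17.3% | 10.7% |
| 0.7 | 5.49 | 16 | 40.3% | 31.8% | 23.7% |

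Simulated t-tests give about 11%, 15%, 26% and 42% with no cycle; 6%, 9%, 17% and 31% with 30% weekly; and 3%, 4%, 11% and 23% with 50% weekly. Formula and simulation agree to within about two percentage points, and Wilcoxon results lie within about 2.5 points of the t-test.

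**Step 4: where the direction changes.** The default is exact when VIF × (1 − w) = 1. Using VIF ≈ (1 + ρ)/(1 − ρ), that is ρ ≈ 0.18 for w = 30% and ρ ≈ 0.33 for w = 50%. Below those values the test is conservative; above them it is liberal.

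**Step 5: the alternatives.** With regression on period and day of week, AR(1) errors give about 6% rejection. The fit matters: one simulation gave 6%, 6%, 7% and 11% at ρ = 0.2, 0.3, 0.5 and 0.7, while a restricted maximum likelihood fit that allows for a 30-day gap between the periods stayed between 5% and 7% in 3,000 runs per setting. Newey-West with 7 lags gave 7%, 8%, 10% and 14%.

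**The case against.** The strongest reply is that no passage assigns a test, or the day as analysis unit, to this endpoint; the tests sit in a general-methods paragraph, and a separate health economic analysis is promised. That is fair as far as it goes. But a default that applies unless something else is specified is the plan for this endpoint, nothing else is specified, and a daily value compared between periods leaves no other evident unit.

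Three stronger readings are tempting and not supported:

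- A reader might infer that the plan would usually declare a spurious difference. The weekly-cycle columns show otherwise: at weak correlation with a strong cycle the test is conservative.
- A reader might infer that confidence intervals for bed availability would be too narrow. The SAP plans 95% intervals only for adverse-event differences, so no planned interval is affected.
- A reader might infer that modelling the correlation makes the period comparison sound. It does not. With one switch at one hospital, period coincides with calendar time under any error model, and that remains the larger threat to interpretation.

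It also stands that every size above rests on an assumed correlation. The overnight-stay mechanism is weaker for the ED, and the expected minimum stay in Protocol 9.3 describes study subjects rather than all occupants of a unit. The study calls itself a pilot, and this is one of 16 secondary endpoints.

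**Conclusion.** The point holds as a miscalibration of p-values for one secondary endpoint. Applied to the daily series, the SAP's default tests have an error rate that depends on two features the plan does not model. Over lag-1 correlations of 0.2 to 0.7 it ranges from about 11% to 42% with no weekly cycle, 6% to 31% with 30% of variance weekly, and 3% to 23% with 50% weekly. The p-values are too favourable under moderate or strong correlation, and probably less so for the ED. This rests on an AR(1) pattern, about 90 days per period and assumed correlations, because the documents supply none. The primary length-of-stay analysis is not affected. The change should be made, but it does not threaten the trial's main conclusion.

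**What to change.** In SAP 7.9, state that each unit's daily series is analysed by regression on period and day of week with AR(1) errors, and name the fitting method (restricted maximum likelihood behaves well at this length). This replaces the two-sample tests for this endpoint. Keep Newey-West standard errors as a sensitivity analysis only, with the lag stated: with 7 lags they still reject 8% to 14% of the time for correlations of 0.3 to 0.7. The simpler alternative is to report the series descriptively, without p-values. Either way, add a sentence that period is confounded with calendar time whichever model is used.

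The cost is two or three sentences in the SAP and slightly more programming, with no new data. The p-values will be less favourable than the default's if correlation is moderate or strong.
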